^a Visit/dosing windows of ±3 days on either side of the scheduled visits/dosing are permitted. In case of a delayed or missed dose, the investigator should return subjects on the original visit/dosing schedule in relation to Day 1 for subsequent doses. The window of ±3 days is relative to Day 1 and applicable for all subsequent visits/dosing. The minimum of time between doses should be no less than 4 days and no more than 10 days. Subjects do not need to return to the clinical site for dosing on weeks without study visits noted above if subject/caregiver completes study drug administration at home. See footnote “r” below.

^b Visit window of ±5 days. For subjects who prematurely discontinue study drug, the End of Treatment (EOT) visit should be completed within 14 days of withdrawal and follow-up visits should be completed at 8 weeks (Safety FU) and 14 weeks (PK & ADA FU) after the last dose of study drug, where possible. Subjects should continue to complete study assessments as outlined above where possible, with the exception of study drug administration. Anti-drug antibody sample and PK sample collection will not need to be completed if study drug is prematurely discontinued other than at the PK & ADA FU visit.

^c

All subjects who do not achieve cDAPSA low disease activity (cDAPSA ≤ 14) for 2 consecutive visits starting at Week 24 (e.g. at Week 20 and Week 24) will be required to discontinue study drug as described in Section 7.1. Participation in the study should be continued, with EOT visit and assessments as described in Section 4.1 and in footnote b and n.

^d Vital signs include measurements of temperature, respiratory rate, systolic and diastolic blood pressure, and pulse. Measurements should be taken in a sitting position after 5 minutes' rest.

^e Electrocardiograms in triplicate will be recorded (one minute apart) after subject has been supine for at least 5 minutes.

^f Chest x-ray (posterior/anterior or anterior/posterior) will be performed at screening in subjects who do not have a chest x-ray available within 3 months of screening. Women of childbearing potential must have a negative pregnancy test before an x-ray is performed.

^g Serious adverse events should be recorded from the signing of informed consent through the Safety Follow-up visit (ie, 8 weeks after the last dose of study drug); adverse events will be recorded from Day 1 (ie, administration of study drug) until 4 weeks after the last dose of study drug.

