To assess the safety and tolerability of izokibep as measured by the incidence of TEAEs, events of interest, SAEs, and clinically significant laboratory values and vital signs	
 • TEAEs, events of interest, and SAEs • Laboratory values and vital signs at collected timepoints
To assess the immunogenicity of izokibep as measured by the presence of ADAs	
 • Treatment-emergent ADAs
Exploratory	

To demonstrate that 1 or both regimens of izokibep (160 mg QW and 160 mg Q2W) are efficacious compared to placebo up to Week 16 and to estimate the efficacy of each regimen after week 16, as measured by:
 
 • Proportion of subjects achieving 70% improvement in ACR core set measurements (ACR70) at Weeks 16, 24, and 52 • Change in DAS28-CRP at Weeks 16, 24, and 52 as compared to baseline • Change in DAPSA score at Weeks 16, 24, and 52 as compared to baseline • Change in clinical DAPSA (cDAPSA) score at Weeks 16, 24, and 52, as compared to baseline • Proportion of subjects achieving DAPSA and proportion of subjects achieving cDAPSA low disease activity or remission at Weeks 16, 24, and 52 • Proportion of subjects achieving DAPSA and proportion of subjects achieving cDAPSA remission at Weeks 16, 24, and 52 • Change in PASDAS at Weeks 16, 24, and 52 as compared to baseline • Proportion of subjects achieving 75% or greater reduction in PASI score from 	
 • ACR70 at Weeks 16, 24, and 52 • Change in DAS28-CRP at Weeks 16, 24, and 52 • Change in DAPSA at Weeks 16, 24, and 52 • Change in cDAPSA at Weeks 16, 24, and 52 • DAPSA/cDAPSA \leq 14 at Weeks 16, 24, and 52 • DAPSA/cDAPSA \leq 4 at Weeks 16, 24, and 52 • Change in PASDAS at Weeks 16, 24, and 52 • PASI75 at Weeks 16, 24, and 52 with \geq3% BSA psoriasis at baseline

Objectives	Endpoints

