6.8.3. Prohibited Medications

The following medications are prohibited from enrollment through Week 52, unless otherwise specified or unless study drug has been permanently discontinued:

1. all other biologic therapies with a potential therapeutic impact on PsA including but not limited to:
 - a. IL-17 receptor inhibitors (eg, secukinumab, ixekizumab, bimekizumab, brodalumab)

- b. biologics with potential for or known association with progressive multifocal leukoencephalopathy (ie, natalizumab, rituximab, efalizumab)
 - c. TNFi (eg, adalimumab, etanercept, infliximab, golimumab)
- 2. IM or oral gold
- 3. cytotoxic agents (eg, cyclophosphamide, D-penicillamine)
- 4. any other immunomodulatory therapy (eg, cyclosporine, azathioprine, tacrolimus, IV gamma-globulin, or Prosofia column therapy)
- 5. JAK inhibitors (eg, tofacitinib, upadacitinib)
- 6. other conventional systemic DMARDs (csDMARDs) (other than methotrexate, leflunomide, hydroxychloroquine, and sulfasalazine with stable doses as specified in [Section 6.8.2](#))
- 7. IA hyaluronic acid injections
- 8. IA, IM, or IV corticosteroids including adrenocorticotropic hormone. Corticosteroid injections into trigger points, tender points, bursae, or entheses are not permitted
- 9. other psoriasis treatments not listed above (eg, mycophenolate mofetil, retinoids, fumarates, vitamin D analogues, keratolytics, coal tar, or phototherapy [eg, PUVA, UVA, UVB, high potency topical corticosteroids unless indicated for injection site reactions to be used only on affected reaction area])
- 10. medium or high potency narcotic analgesics (eg, morphine or morphine-derived medications, fentanyl, hydromorphone, levorphanol, meperidine, methadone, or hydrocodone). Tramadol or combination formula of paracetamol with codeine or with hydrocodone are permitted at stable doses as specified in Section 6.8.2
- 11. live vaccines (during the study and for 12 weeks following the last dose of study drug)
- 12. any investigational agents

7. Discontinuation of Study drug and Subject Discontinuation/Withdrawal

Discontinuation of specific sites or of the study as a whole are detailed in [Section 10.1.8](#).

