7.1. Discontinuation of Study Drug

In rare instances, it may be necessary for a subject to permanently discontinue study drug. The reason for permanent discontinuation of study drug will be documented. If study drug is prematurely and permanently discontinued, the subject will be encouraged to remain in the study to be evaluated for safety and efficacy. Subjects should continue to complete study assessments as outlined in the SoA ([Section 1.3](#)) where possible, with the exception of study drug administration, and anti-drug antibody sample and PK sample collection. Reasons for removal from study drug include any of the following:

- subject request
- death
- lost to follow-up
- termination of study by sponsor
- emergency unblinding
- liver chemistry stopping criteria (see [Section 7.1.1](#))
- serious infections
- the subject becomes pregnant while on study drug
- malignancy
- subject develops CTCAE v5.0 grade 3 or higher SAE or AE(s) that is considered by the investigator to be related to study drug
- subject develops an illness that, in the opinion of the Investigator, would interfere with his or her continued participation, if the risk of continuing with study drug outweighs the potential benefit
- subject uses prohibited concomitant medications, as defined in [Section 6.8.3](#), that may present a risk to the safety of the subject in the opinion of the Investigator or the Medical Monitor
- subject is non-compliant with TB prophylaxis (if applicable) or develops active TB at any time during the study
- subject is significantly non-compliant with study procedures which would put the subject at risk for continued participation in the trial as determined by the Investigator or Medical Monitor
- subjects with disease progression or not responding to treatment are to be withdrawn from study drug treatment based on Investigator's discretion

- Starting at Week 24, subjects who have not met clinical Disease Activity for PsA (cDAPSA) low disease activity ($cDAPSA \leq 14$) at 2 consecutive visits (e.g. at Week 20 and Week 24) will be discontinued from study drug and can receive standard of care treatment as deemed appropriate by the Investigator.

Subjects with newly diagnosed IBD during the study must:

- discontinue study drug and be followed-up until resolution of active IBD symptoms
- be referred, as appropriate, to a health care professional treating IBD, such as a gastroenterologist

[figure not shown]

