### **3.1.4. Handling of Intercurrent Events to Reflect the Clinical Question of Interest**

The treatment strategy approach for the estimand will be used in general, so subjects will be included using observed data at Week 16 regardless of treatment discontinuation, concomitant medication, protocol deviations, or other actions. Subjects with missing full ACR50 assessments at Week 16 will be imputed as non-responders (non-response imputation or NRI). Subjects missing one or more components of ACR50 will be included as defined in Section 5.2.1, with subjects having missing ACR50 due to missing components also imputed as non-responders.

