### **6.6.5. Exploratory Analysis**

Exploratory endpoints will be analyzed analogously to primary and secondary endpoints, with the exception of a prespecified alpha-controlling testing strategy. Exploratory endpoints of dichotomous measurements will be analyzed analogously to primary endpoints. Exploratory endpoints of continuous measurements will be analyzed analogously to the secondary endpoint of change in physical function of HAQ-DI from baseline to Week 16. P-values for exploratory endpoints will be considered descriptive and not considered conclusive. A summary table of all primary, secondary and exploratory endpoints will be presented using point estimates only, to visually assess izokibep 160 mg dosed QW, izokibep 160 mg dosed Q2W, izokibep 80 mg dosed Q4W and placebo.

All primary, secondary and exploratory endpoints defined for comparing izokibep 160 mg QW or izokibep 160 mg Q2W to placebo will also be reported for comparing izokibep 80 mg Q4W to placebo.

Dose-response will be investigated through analyses of the primary and secondary endpoints, which will use all four treatment arms (izokibep 160 mg QW, izokibep 160 mg Q2W, izokibep 80 mg Q4W and placebo) in a single analysis for each endpoint. A p-value for the global test of the hypothesis that all groups have identical response rates will be reported for each endpoint, not subject to type I error rate control or any multiple comparison procedure. P-values will also be reported for all pairwise comparisons for each endpoint. Dose-response relationships will be assessed qualitatively from these analyses. Due to the error in dose sequence in the Q2W and Q4W arms, additional investigations will include assessment of endpoints that may be achieved earlier, including ACR20 and PASI75 at week 4 (at which time all subjects received correct dose sequencing).

The following binary endpoints before or on Week 16 will be analyzed analogously to the primary endpoints of ACR50 at Week 16. The number and proportion of subjects for binary

endpoints in each treatment group will be reported without strata along with Clopper-Pearson 95% CI. Common risk difference with Cochran-Mantel-Haenszel weighting will be used to calculate a 95% CI, and p-values from the stratified test will be reported as well. The binary endpoints after week 16 will include number and proportion along with Clopper-Pearson 95% CI without strata according to the four randomized treatment groups. No p-value will be reported.

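### Week 52 response rates pool responses reached on izokibep with those reached after the protocol's mandatory drug stop, and no planned table shows the on-izokibep part

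*SAP*

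**What the plan says.** **Objective.** One exploratory aim in Protocol Section 3 (also in the synopsis) is "to estimate the efficacy of each regimen after week 16, as measured by" a list of endpoints at Weeks 24 and 52.

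**Drug stop.** Under Protocol 7.1, from Week 24 onward, subjects without cDAPSA low disease activity at two consecutive visits "will be discontinued from study drug and can receive standard of care treatment as deemed appropriate by the Investigator". The same section allows withdrawal at any week: "subjects with disease progression or not responding to treatment are to be withdrawn from study drug treatment based on" the investigator's judgement. Protocol 6.8.3 lists other biologics and JAK inhibitors among the drugs "prohibited from enrollment through Week 52, unless otherwise specified or unless study drug has been permanently discontinued", so the ban lifts at the stop. Follow-up does not end there. Footnote b of the Schedule of Activities says: "Subjects should continue to complete study assessments as outlined above where possible, with the exception of study drug administration".

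**Analysis.** SAP 6.6.5 says that "binary endpoints after week 16 will include number and proportion along with Clopper-Pearson 95% CI without strata", by the four randomized groups and without p-values. It also says: "Exploratory endpoints of dichotomous measurements will be analyzed analogously to primary endpoints". The primary rule, in SAP 3.1.4, is that "subjects will be included using observed data at Week 16 regardless of treatment discontinuation, concomitant medication, protocol deviations, or other actions". SAP 5.2.1 turns missing assessments, and only those, into non-response.

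**What else is reported.** SAP 6.2 tabulates by group the subjects who permanently discontinued study medication, those who met the cDAPSA stop criterion, and the reasons for discontinuing treatment. Listings cover discontinuation status and reason (6.2), first and last dose dates (6.7.1) and all efficacy data (6.6.5). SAP 6.7 regroups selected adverse event summaries by treatment received in Period 2. Efficacy has no such regrouping.

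**The concern.** The design itself creates Week 52 data collected off izokibep, possibly on another effective drug. SAP 6.6.5 has no separate rule for discontinuation or new therapy at visits after Week 16. On its natural reading, a response reached on, say, a TNF inhibitor after the mandated stop is counted in the izokibep group's Week 52 rate.

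Discretionary withdrawal can do the same at earlier visits, but the mandatory rule makes it systematic by Week 52. There is no placebo arm after Week 16 against which to judge the figure. What is at stake is interpretation: a reader of the tables could take the Week 52 rate as response to continued izokibep and could not see how much of it was.

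**Working it through.** The plan states no figure on this point, so the check is a chain of text followed by simple arithmetic.

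**1. Does the rule reach Week 52?** SAP 3.1.4 is written for Week 16. Extending it to later visits rests on the analogy clause in SAP 6.6.5 and is an inference. No other section supplies a competing rule: the supplementary analyses in SAP 6.6.2 and 6.6.4 concern Week 16 or earlier.

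**2. Is there time to respond to another drug?**
- Stop at Week 24: 52 − 24 = 28 weeks to Week 52.
- Stop at Week 32: 52 − 32 = 20 weeks.

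Both exceed the 16 weeks to the primary endpoint.

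**3. How far apart are the two summaries?** For one arm, let *s* be the share who have permanently stopped study drug or started another PsA-active therapy before Week 52, *r* the share of those with an observed Week 52 response, and *q* the response rate in the rest.
- Current summary: (1 − s)q + s·r
- Scored as non-response after stop or switch: (1 − s)q
- Difference: s·r

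The documents give none of *s*, *r* or *q*, so all values below are assumptions.

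| s | r | difference |
|---|---|---|
| 0.10 | 0.10 | 0.010 |
| 0.25 | 0.20 | 0.050 |
| 0.40 | 0.35 | 0.140 |

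In an arm of 100 this is 1 to 14 subjects. The 35% ceiling is the low end of the 24-week ACR50 range that Protocol 4.3 gives for current agents. Wider inputs, s = 0.50 and r = 0.45, give 0.225.

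As one worked case, take q = 0.60, s = 0.30, r = 0.20. The current rate is 0.42 + 0.06 = 0.48, against 0.42, and 0.06 / 0.48 = 12.5% of reported responders are off izokibep or on another therapy.

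For scale only: Protocol 9.5 gives a confidence interval half-width of about 10 points for a 45% rate in 100 subjects, and 1.96 × √(0.45 × 0.55 / 100) = 0.098 agrees.

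**4. Is every post-stop response due to another drug?** No. Using the cDAPSA definition in SAP Appendix 2.5, with illustrative values: tender joints 20 to 10, swollen joints 12 to 6, pain 70 to 35, subject's global 70 to 35, investigator's global halved. ACR50 is met. cDAPSA goes from 20 + 12 + 7 + 7 = 46 to 10 + 6 + 3.5 + 3.5 = 23, still above 14. In general, halving all four components leaves cDAPSA above 14 whenever baseline exceeds 28. Some subjects are therefore stopped while ACR50 responders on izokibep. Placebo subjects who cross over can be stopped after 24 − 16 = 8 weeks of izokibep.

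**5. Will the tables show the new therapies?** This is unclear. SAP 6.4.4 counts drugs started by the end of the Treatment Period, which SAP 5.1.3 ends at Week 52 or at early termination or the end-of-treatment visit. That visit is due within 14 days of withdrawal, so by about Week 26 for a Week 24 stop. If the period closes there, drugs started in the remaining 52 − 26 = 26 weeks are left out. If early termination means leaving the study, as in SAP 5.1.4, they are included. Either way the data exist: Protocol 8.2.1 records medication changes to Week 65.

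**The case against.** The strongest reply is that the SAP does what the protocol tells it to do. The synopsis says that efficacy will be summarized by randomized group over 52 weeks, and the primary efficacy analyses use a treatment-policy strategy. That stands. A reader might infer that the Week 52 rate is biased or departs from the protocol. The documents do not support this: the two summaries answer different questions, and each is valid for its own.

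A reader might also infer that the current summary misses the stated objective. That goes too far. The stop is built into every arm, so *regimen* can fairly mean the randomized regimen with its stopping rule, and no document restricts the aim to time on drug. SAP 2.2.3 does not repeat the after-Week-16 wording. What remains is that one natural component of the objective, response while on izokibep, has no table.

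Three further points stand and narrow the request:
- The number stopped is already in the disposition table. It bounds the post-stop responders among discontinued subjects, and the planned listings allow an exact reconstruction. A listing is still not a summary.
- No size is shown. The 35% ceiling comes from current agents generally, not from subjects selected for failing izokibep. Post-stop visits happen only where possible, and a missing assessment counts as failure. The true difference may be well below the upper figures.
- Continuous endpoints at Week 52 share the feature and are not addressed here.

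The protocol's durability and incremental-response objectives do not fill the gap. They split by Week 16 response, not by drug status, and the SAP sets out no analysis for them.

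**Conclusion.** The point holds as an inexpensive improvement, not as an error in the planned analysis. On the natural reading of SAP 6.6.5, Week 52 binary response rates can include responses reached off izokibep, and no planned efficacy table separates them. The conclusion rests on extending the primary rule to later visits by analogy. If the sponsor intends another rule, the SAP needs to state it.

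The documents do not determine the size. The range of 1 to 14 points follows only from the assumed inputs and should not be read as an estimate of inflation. These endpoints are exploratory and carry no p-values. The mandatory stop begins at Week 24, so no Week 16 test, power figure or error rate is affected.

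**What to change.** In SAP 6.6.5, for Week 52 and any other binary endpoint after Week 24:

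1. Add a companion summary that scores a subject as a non-responder after permanent study drug discontinuation or after starting another PsA-active therapy (for example a biologic, JAK inhibitor, new csDMARD, or intra-articular, intramuscular or intravenous corticosteroid). Cover at least ACR50, PASI90, enthesitis resolution, MDA, ACR20 and PsAID response.
2. Keep the current summary beside it, state that it uses observed data regardless of discontinuation or new therapy, and label it *randomized regimen including any later standard of care*.
3. Add a count by arm of subjects who started another PsA-active therapy by Week 52, including after an early end-of-treatment visit. The number stopped needs no new table.

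The stopping rule, data collection and every Week 16 analysis stay as they are. The cost is SAP wording, a little more programming, and a rule for classifying PsA-active therapy fixed in advance. Rates in the added summary will be the same or lower. It scores as failures some ACR50 responders stopped for cDAPSA above 14, subjects stopped for adverse events, and crossover subjects stopped after about 8 weeks of izokibep. For that reason both summaries should be shown.
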